4.1 Description of Study Design

This is an open-label, phase I pilot study to primarily evaluate the feasibility and safety of bronchoscopic cryo-immunotherapy (BCI) of peripheral lung tumors in patients with non-small cell lung cancer or suspected non-small cel lung cancer who are undergoing a standard-of-care bronchoscopy for palliative and/or diagnostic purposes. Dose escalation will proceed using a standard 3+3 design.

4.2 Study Endpoints

4.2.1 Primary Study Endpoints: Feasibility and Safety

- Each patient will be classified as having successfully undergone BCI or not. Feasibility of BCI is defined as successfully performing BCI in at least 80% of patients in whom BCI is attempted. Successful performance of BCI will require identification of the target peripheral lung tumor by radial endobronchial ultrasound within 20 minutes followed by completed cryoablation of target tumor. The target tumor will have freeze-thaw cycles applied every one centimeter of the largest diameter. Additional BCI features will be described as follows:
 - a) Ability of radial endobronchial ultrasound to identify peripheral lung tumor
 - b) Length of time to perform BCI
 - c) Length of time of fluoroscopy exposure during BCI
- 2) Dose-limiting toxicities (DLT) will be used to guide the dose-escalation procedure and determine the maximum tolerated dose. A DLT is defined as any of the following occurring up to 7 days post-BCI:
 - Grade 2 or 3 bleeding, based on the following scale (34):
 - a) Grade 0: absence of bleeding
 - b) Grade 1: bleeding requiring suctioning to clear
 - c) Grade 2: bleeding requiring an endoscopic procedure (iced saline, 1:20,000 topical epinephrine, or bronchial occlusion)
 - d) Grade 3: severe bleeding (>100cc total volume). Severe bleeding will also be defined as bleeding which cannot be controlled endoscopically, requires ICU admission or interventional radiology/ surgical intervention, or results in respiratory or hemodynamic instability (34)
 - Pneumothorax necessitating tube thoracostomy; recorded features of pneumothorax to include:
 - a) size
 - b) associated symptomatology
 - c) respiratory impairment
 - d) need for chest tube placement
 - Any NCI CTCAE (33) grade 3, 4, or 5 adverse events, which may be possibly, probably, or definitely related to BCI

4.2.2 Secondary Study Endpoints: Immune Analysis

CONFIDENTIAL

1) Assess BCI Induced Anti-Tumor Immune Responses in Peripheral Blood

Research Samples: Peripheral blood will be collected by the investigatory team prior to BCI on the day of procedure, and at approximately 7 days and 14 days after BCI (± 3 days). Specimens may be processed in the [name] Environmental Lung Disease Laboratory, the [name] Translational Lung Biology Laboratory, or in the [name] Laboratory on the campus of the New York University Langone Medical Center/Bellevue Hospital Center.

Flow cytometry: Peripheral blood samples will undergo Ficoll-Paque separation. The buffy coat containing peripheral blood mononuclear cells (PBMCs) will be isolated, and then washed with phosphate buffered saline. Isolated PBMC will undergo staining with antibodies against the markers described in Table 1 (Section 2.1: Background Information and Relevant Literature – Subsection VI Biomarkers to Assess for BCI Induced Anti-Tumor Immune Response) in [name] laboratory in the Perlmutter Cancer Center at NYU School of Medicine.

Data will be acquired on a BD Symphony A5 flow cytometer, and analyzed using FlowJo software and various R-based bioinformatics algorithms developed previously by [name] and colleagues. The 30-parameter flow cytometry panels we plan to use (Table 1) will query multiple markers of activated cells (including a broad range of cytokines), and multiple markers associated with immune checkpoints (along with markers of T-cell differentiation). To ensure that our results do not reflect global T-cell activation or exhaustion, in follow-up experiments, we will substitute a cocktail of peptide MHC Class I multimers ("tetramers") against influenza and EBV responses into panel 1 (the cocktail will cover various epitopes and HLA-types) and stimulate a parallel aliquot of cells from panel 2 with a CEF (CMV/EBV/influenza) cocktail of peptides or the same tetramer cocktail used for Panel 1.

mRNA analysis: We will also be assessing a variety of other immune biomarkers from peripheral blood utilizing the NanoString[™] platform, including cytokine gene expression, that may allow for the establishment of a variety of peripheral blood biomarkers to correlate with the effects of BCI in advanced NSCLC. Once sorted, the CD8+ and CD4+CD25- cells (non-Treg cells) will be processed for RNA extraction and NanoString[™] mRNA quantitation. RNA extraction will be performed using the MARIS technique to insure RNA quality after sorting (35). We are particularly interested in determining gene expression of proteins involved in T cell activation and immune regulation, such as CTLA-4, PD-1, OX-40, TIM-3, IL-10, TGF-ß, IL-2, MHC-II and TNF-α. The transcriptome data will be processed in collaboration with the Biostatistics Division led by [name] at the NYU School of Medicine to calculate the relative expression of the key genes of interest previously noted. The NanoString[™] platform offers the convenience of straightforward high-throughput mRNA quantitation using RNA barcodes to probe and count mRNA transcripts of interest (28). Our preliminary analysis will be conducted with the pre-designed Oncolmmune[™] Profile panel, which measures 770 gene targets most relevant in tumor immunobiology.

2) Investigate BCI Association with PD1 phenotype of Effector T cells in NSCLC

Research Samples: In addition to peripheral blood specimens as described previously, BAL fluid will be collected from regions of the primary tumor and of the distal portion of the same lung.

Using a subset of samples from enrolled subjects enrolled with sufficient BAL specimens, we will perform single-cell RNA sequencing on sorted CD3+ T cells from BAL and PBMCs obtained at the time of BCI. This approach will be repeated in PBMC after 7 and 14 days post BCI. The percentage of PD-1 expressing T lymphocytes will be determined in CD4⁺ and CD8⁺ cells from both BAL and PBMC compartments. PD1⁺ cell percentage and transcriptome will be compared between responder categories. RNA sequencing and subsequent data analysis will be performed in the Genomic Technology and Bioinformatics Cores of NYU School of Medicine.

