| Brief Summary | This is a first-in-human, safety and feasibility study of bronchoscopic cryo- immunotherapy (BCI) of peripheral lung tumors in advanced non-small cell lung cancer (NSCLC) and suspected NSCLC. BCI has the potential to stimulate anti-tumor immune responses. Pre- and post-BCI peripheral blood samples will be analyzed to assess for anti-tumor immune responses. Post- BCI peripheral blood will be collected 7 and 14 days after the procedure. Additionally, pre-BCI bronchoalveolar lavage (BAL) specimens will be collected to correlate PD-1 phenotype on pre-BCI BAL lymphocytes by single cell RNA sequencing and BCI-induced anti-tumor immune responses. | | |
| Phase | Phase I | | |
| Objectives Primary: • Establish safety and feasibility of BCI and determine the maximu tolerated dose (MTD) (i.e., freeze duration) Secondary: | | | |
| Assess the extent of BCI-induced anti-tumor immune respons | | | |
| Methodology Dose-escalation trial using a 3+3 design Primary: Feasibility and Safety | | | |
| | Feasibility: successful performance of BCI in at least 80% of participants in whom BCI is attempted Safety endpoints: Dose-limiting toxicity (DLT), defined as incidence of bleeding complications and pneumothorax, length of time to perform BCI, length of fluoroscopy exposure during BCI, and other adverse events | | |
| Endpoints | Secondary: Immune Analysis and Tumor Response Changes in peripheral blood CD8⁺ T cells expressing a combination of Ki67⁺,PD-1+, HLA-DR⁺, CD38⁺, and Bcl-2^{low} after BCI Changes in peripheral blood lymphocyte gene expression after BCI, which will be assessed by the PanCancer OncolmmuneTM profile panel, a 770-plex gene expression panel covering innate and adaptive immune responses (NanoString® Technology, Seattle, WA) Correlation of PD-1 phenotype of pre-BCI BAL lymphocytes by single-cell RNA sequencing and BCI-induced anti-tumor immune responses. | | |
| Study Duration 12 months | | | |
| Participant Duration | 14 days | | |
| Duration of IP administration | BCI will be performed once at the time of a standard-of-care bronchoscopy for another indication. BCI is anticipated to take approximately 15-25 minutes. | | |

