5.6 Duration of Study Participation

The total duration of study participation is 14 days. BCI will be performed at time of standard of care bronchoscopy on day 0. Peripheral blood will be collected by the investigatory team prior to BCI on the day of procedure, which will be drawn off the intravenous catheter inserted for the standard of care bronchoscopy to avoid a separate blood draw whenever possible. The investigatory team will also collect blood samples at approximately 7 days and 14 days after BCI (± 3 days). During each blood

draw, the volume of blood collected will be approximately 2 teaspoons (10 ml). This will occur at routine standard of care follow up clinic visits whenever possible. Alternatively, the investigatory team will collect blood samples at approximately 7 days and 14 days after BCI at the Perlmutter Cancer Center.

Total Number of Participants and Sites

- Total number of participants: 15-24
- Sites: New York University Langone Medical Center

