7.1.2 Standard of Care Study Procedures

Pre-BCI screening:

- Medical history (including cancer and cancer treatment history, co-morbidities, functional status, and social history)
- Medication and treatment history (specifically if patient is on a platelet inhibitor other than aspirin
 or anticoagulant), and if patient has previously or is currently receiving chemotherapy, radiation
 therapy, or immunotherapy.
- Physical examination (vital and full physical exam will be performed by clinical team prior to determining patient's fitness for undergoing bronchoscopy
- Chest CT assessment to evaluate for the presence of a bronchus or airway path leading directly to the peripheral lung tumor
- Screening laboratory evaluation as described in Section 7.2
- Pre-BCI blood collection for immune analysis

During bronchoscopy:

• Bronchoalveolar lavage (BAL) will be performed in two locations, which are the regions of the primary tumor and of the distal portion of the same lung. BAL is a standard of care component of routine bronchoscopy for lung cancer.

CONFIDENTIAL

- If there is no pre-existing biopsy-proven non-small cell lung cancer diagnosis, on-site pathology review of a tissue biopsy obtained during bronchoscopy may be performed, if technically feasible or if the patient does not have high risk features for possible non-small cell lung cancer (see above).
- After the standard-of-care portion of the bronchoscopy is complete, the peripheral tumor will need to be identified by radial EBUS. If the peripheral tumor cannot be identified within 20 minutes, then BCI will not be performed.
- BCI will be performed in eligible candidates

Post-BCI:

- Monitor for any adverse events from day 0 to day 7 Post-BCI blood collection for immune analysis on day 7 ± 3
- Post-BCI blood collection for immune analysis on day 14 ± 3
- Patients who undergo BCI and are found not to have non-small cell lung cancer will be monitored for adverse events from day 0 to day 7 and be followed up at a standard of care pose-bronchoscopy visit within 7 ± 3 days. These patients will not have post-BCI blood collected.

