10.2 Statistical Hypotheses

- 1) BCI will be feasible and safe, with a maximum tolerated dose to be determined in this trial.
- 2) Post-BCI peripheral blood will demonstrate an increase in the percent of CD8⁺ T cells expressing a combination of Ki67⁺, PD-1+, HLA-DR⁺, CD38⁺, and Bcl-2^{low} compared to pre-BCI peripheral blood CD8⁺ T cells.
- 3) CD8+ T cell responses to BCI will be greater among subjects with high PD-1 expressing T cells in BAL effluent.

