10.4 Description of Statistical Methods

10.4.1 General Approach

- Continuous data will be summarized with means and standard deviations.
- Categorical data will be summarized with frequencies and percentages.
- *P* values will be considered statistically significant at the 0.05 level. Note that the study is designed to determine the MTD, and thus is not powered to detect statistically significant differences in any of the secondary outcomes.

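### Section 4.2.2 compares BAL PD-1 percentage and transcriptome between responder categories that are never defined; a full-scale rank correlation should be the main analysis

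*Combined protocol and SAP*

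**What the plan says.** Four parts of the document describe how BAL PD-1 is to be related to the response to BCI, and they differ.

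- **Section 4.2.2, item 2.** "Using a subset of samples from enrolled subjects enrolled with sufficient BAL specimens, we will perform single-cell RNA sequencing" on T cells from BAL and blood. The PD1+ "cell percentage and transcriptome will be compared between responder categories". The size of the subset is not given.
- **Protocol Summary, secondary endpoints.** "Correlation of PD-1 phenotype of pre-BCI BAL lymphocytes by single-cell RNA sequencing and BCI-induced anti-tumor immune responses". This needs no categories.
- **Section 10.2, hypothesis 3 (and section 3.2, item 2).** "CD8+ T cell responses to BCI will be greater among subjects with high PD-1 expressing T cells in BAL effluent". Here PD-1 carries the label high and the CD8+ response is left whole.
- **Section 10.4.4.** A Wilcoxon signed-rank test is applied to CD8+ responses and BAL PD-1 expression, with no categories.

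The subset is bounded by enrolment (section 5.6: "Total number of participants: 15-24"). It shrinks further because treated patients found not to have NSCLC contribute no response (section 7.1.2: "These patients will not have post-BCI blood collected"). On significance, section 10.4.1 says that P "values will be considered statistically significant at the 0.05 level" and adds that the study is not powered for secondary outcomes. Section 10.5 repeats that limitation.

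**The concern.** BAL PD-1 is a percentage. The CD8+ response in section 10.2 is a change in a percentage. Both are continuous, and no clinical or regulatory reason is given for grouping either.

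If responders are defined by cutting the CD8+ change, two things follow. First, the ordering of participants within each group is lost, so a real association is more likely to be missed. Second, the result depends on where the cut falls, on whether day 7 or day 14 is used, and on which marker combination counts. With no definition on file, all of these can be settled after the data are seen.

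This matters because section 10.5 offers the results as input to the design of later studies of BCI with anti-PD-1 therapy, and the link between BAL PD-1 and response bears directly on that. Correcting the test in section 10.4.4 would not remove the problem: the grouping in section 4.2.2, including for the transcriptome, would remain.

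**Working it through.** **1. The plan's own power figure.** Section 10.5 gives 15 subjects, about 80% power, a difference of 0.75 SD and a within-subject correlation of 0.5. The SD of the difference is SD × √(2(1 − 0.5)) = 1 SD, so the standardised effect is 0.75. By normal approximation, N = ((1.960 + 0.842)/0.75)² = 13.95, so 14. By the noncentral t, N = 16 (80.1% power). At N = 15, power is 77.1% (paired t) or 82.8% (normal), two-sided. The figure reproduces within its own approximations. It concerns the paired pre/post change only; no power figure is given for the BAL analysis.

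**2. Does section 10.4.4 already supply a sound uncut analysis?** No. A signed-rank test on pairs (CD8+ response, BAL PD-1) asks whether the differences between the two quantities centre on zero. Rescaling one of them changes the answer, while their association is unaffected. It also does not cover the transcriptome.

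**3. Cost of a cut, if the CD8+ change is what is cut.** Inputs:
- Alpha 0.05 (section 10.4.1); two-sided is assumed.
- n = 12 to 24. The upper limit is from section 5.6; the rest is assumed.
- True correlation r = 0.4 to 0.7, bivariate normal: assumed.
- Share of responders 70% or 50%: assumed. Section 2.1 (VI) reports that about 70% of a cohort on PD-1/PD-L1 axis inhibitors had a 1.5-fold rise in Ki67+ CD8+ cells. The trial does not adopt that threshold, so it serves only as an illustration.

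The comparison, by simulation, is Spearman correlation on full scales against an exact rank-sum test of BAL PD-1 between responders and non-responders.

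| n | r | Cut | Full scale | After cut | Loss (points) |
|---|---|---|---|---|---|
| 12 | 0.4 | 70/30 | 22% | 14% | 8 |
| 15 | 0.5 | 70/30 | 44% | 25% | 19 |
| 15 | 0.6 | 70/30 | 62% | 36% | 26 |
| 15 | 0.7 | 70/30 | 80% | 51% | 29 |
| 15 | 0.6 | 50/50 | 62% | 40% | 22 |
| 24 | 0.5 | 70/30 | 66% | 42% | 24 |
| 24 | 0.6 | 70/30 | 85% | 60% | 25 |

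Repeat runs agree within a point or two. At n = 15 a 70/30 cut leaves 0.30 × 15 = 4.5 people in the smaller group; the table takes 5, and with 4 the loss is somewhat larger. With no true association, Spearman rejects about 5% of the time and the rank-sum test about 4%, so test size does not explain the gap.

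**4. Sensitivity.** A Pearson correlation against a two-group t-test with a median split gives a loss of 7 to 28 points for n = 10 to 15 and r = 0.4 to 0.7. Outside these settings the range widens. The loss is about 3 points at n = 8 to 10 with r = 0.3, where power is near its floor, and about 3 at n = 24 with r = 0.8, where it is near its ceiling. It exceeds 40 points in some settings where the smaller group holds only a quarter to a third of participants.

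**5. Very small subsets.** The smallest two-sided exact rank-sum p-value is 2/C(n, k), with k in the smaller group. For n = 7, k = 3 it is 2/35 = 0.057; for n = 9, k = 2 it is 2/36 = 0.056. In such subsets the 0.05 level cannot be reached whatever the data show.

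**The case against.** The strongest objection is that the document never says the CD8+ response is cut. A tumor-response reading is open: the Summary heads the secondary endpoints as covering immune analysis and tumor response, section 7.3.4 collects tumor sizes for up to a year, and the reference list includes a tumor-response guideline. Tumor-response groups are categorical by convention, and the power comparison above would not apply to them. This stands as a limit on the point. The CD8+ reading is better supported, because the Summary and sections 3.2 and 10.2 all pair BAL PD-1 with the immune response, and no tumor-response criterion is specified anywhere. It remains an inference.

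A reader might also infer from the word high in hypothesis 3 that BAL PD-1 is cut as well. The text does not support that: no cut-point or two-group test is given, and the sentence fits a steadily increasing relation equally well.

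It can fairly be said that an uncut analysis is already described. The Summary's correlation is one, but no method is attached to it, and the method in section 10.4.4 does not estimate association.

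Finally, secondary outcomes are declared not powered. That limits the consequence. It is not a reason to discard information when keeping it costs nothing.

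**Conclusion.** The firm finding is that the responder categories are undefined and that section 4.2.2 conflicts with the Summary and with sections 10.2 and 10.4.4. The dichotomisation is conditional: if the categories come from the continuous CD8+ change, the cut costs roughly 8 to 29 points of power for PD1+ percentage under assumed bivariate normal data, r = 0.4 to 0.7 and n = 12 to 24. Correlation, subset size and cut point are all absent from the plan.

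Two stronger readings are tempting and not supported. One is that 8 to 29 points is a bound or a cost fixed by the plan; other plausible inputs give about 3 to over 40. The other is that these figures describe the transcriptome comparison. The loss of ordering applies there too, but a single-outcome power figure does not carry over to many genes, and the plan does not address that multiplicity.

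The MTD and feasibility conclusions are unaffected. This is worth correcting in an exploratory secondary analysis.

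**What to change.** In section 4.2.2:

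1. Make the main analysis a Spearman correlation, with a 95% confidence interval, between BAL PD1+ percentage (CD4+ and CD8+ separately) and each participant's continuous pre-to-post CD8+ change. Name the time point and the marker combination in advance.
2. For the transcriptome, aggregate cells to one value per participant per gene and use the same continuous change as the covariate in place of a responder factor.
3. Keep any responder split as a descriptive display with a prespecified definition. If tumor response is meant, say so and state the criterion.

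Align the Summary and sections 3.2, 10.2 and 10.4.4 with this. Hypothesis 3 can state that CD8+ responses increase with the percentage of PD-1 expressing T cells in BAL, and the signed-rank test should be removed for this question.

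The cost is wording only: samples, assays and participants are unchanged. A correlation is slightly less simple to present than two groups, which the descriptive display covers. The analysis should still be labelled exploratory.

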4.2.3 Sub-Set Analysis and Exploratory Endpoints

- Investigation of changes in peripheral blood CD8⁺ T cells displaying a combination of Ki67⁺, PD-1+, HLA-DR⁺, CD38⁺, and Bcl-2^{low} after BCI at each dose level. This sub-set analysis will investigate if there is an optimal freeze time duration for inducing anti-tumor immune responses.
- 2) Investigation of changes in peripheral blood CD8⁺ T cells displaying a combination of Ki67⁺,PD-1+, HLA-DR⁺, CD38⁺, and Bcl-2^{low} after BCI at each dose level. This sub-set analysis will investigate if the combination of cryoablation and current active cancer treatment will lead to enhanced increases in percent of peripheral blood CD8⁺ T cell expression of PD-1 and Ki67 and/or CD8⁺ T cells displaying an activated effector-like phenotype.

5 Study Enrollment and Withdrawal

5.1 Inclusion Criteria

In order to be eligible to participate in this study, an individual must meet all of the following criteria:

- Biopsy-proven, advanced, inoperable non-small cell lung cancer (stages IIIA/B/C and IVA/B based on the 8th edition TNM staging guidelines) or suspected inoperable non-small cell lung cancer (stage as defined above) who may undergo on-site pathology review of tissue specimen obtained at time of diagnostic and staging bronchoscopy.
 - If on-site pathology review is not feasible or is unable to confirm the diagnosis of nonsmall cell lung cancer, patients with high-risk features for the diagnosis of non-small cancer including past or current cigarette smoking, history of COPD, spiculated lesion with bronchus sign on chest CT, presence of mediastinal/hilar adenopathy or evidence of distant metastatic disease on chest CT scan or PET CT scan may be included.
- Pre-procedure chest CT scan with the presence of an airway path leading directly to the peripheral lung tumor (also known as a "bronchus sign"), and the peripheral lung tumor will need to be visualized by radial endobronchial ultrasound at time of bronchoscopy
- Undergoing bronchoscopy for diagnostic and/or palliative purpose unrelated to this study
- Age of 22 years or older
- Ability to provide informed consent
- Concomitant chemotherapy, immunotherapy, and/or radiation therapy are allowed
- ECOG performance status of ≤2

